9.3 Populations for Analysis

The set of enrolled subjects consists of all subjects who signed the informed consent form and were assigned a subject identification number.

The set of randomized subjects consists of enrolled subjects who were assigned a randomized treatment group.

The set of treated subjects consists of all randomized subjects who take study therapy (rimegepant or placebo).

9.4 Statistical Methods

9.4.1 Demographic and Baseline Characteristics

Tabulations of demographic and baseline characteristics are made for: subjects randomized but not treated; subjects randomized and treated; and overall. A separate set of tabulations are made for subjects enrolled but not randomized.

9.4.2 Primary Endpoint(s)

The SPID-2 will be calculated by multiplying the PID score (difference between NRS at each time point and baseline NRS) at each post-dose timepoint by the duration (in hours) since the preceding timepoint, then summing the values over the 2 hours. This is analyzed on the treated population using an analysis of covariance (ANCOVA) model that includes the baseline NRS (0-10) value as a covariate, and main effects for treatment group and stratification factor (use of daily medications / oral devices to reduce the intensity of TMD symptoms).

The least squares mean (LS mean), standard error (SE), and 95% confidence interval (CI) for each treatment group will be reported, as well as the difference estimate (rimegepant - placebo), SE, 95% CI, and p-value.

Intercurrent events will be treated as failures, with the assumption that the subject does not improve once the intercurrent event occurs. In the event a subject uses a non-study rescue medication on or before 2 hours post-dose, all data points after rescue medication was administered will be set to the last available observation prior to rescue medication usage (RM = Rescue medication use: F = Failure). Likewise, if a subject fails to log their pain score at any time after study drug is administered, through 2 hours post-dose, this data will be imputed to the last available observation (NC = Non-completers; F = Failure).

Sensitivity analyses will be described in the SAP.

9.4.3 Secondary Endpoint(s)

If the primary endpoint test is significant at alpha ≥ 0.05 , then the secondary endpoints will be analyzed at an alpha level of ≥ 0.05 using Hochberg's procedure. Secondary endpoints will be analyzed on the treated population.

9.4.3.1 SPID-24

The SPID-24 will be analyzed in the same manner as the primary endpoint, with the SPID calculated by multiplying the PID score at each post-dose timepoint by the duration (in hours) since the preceding timepoint, then summing the values over the 24 hour period.

9.4.3.2 Change from Baseline of Pain on NRS

The change from baseline of pain on NRS score at 2 hours post-dose will be analyzed with a generalized linear mixed effect model that includes subject as a random effect, the baseline NRS (0-10) value as a covariate, and fixed effects for treatment group, stratification factor (use of daily medications / oral devices to reduce the intensity of TMD symptoms), scheduled time point, and time point by treatment group interaction. Time points included in the model are nominally at 15, 30, 45, 60, 90 and 120 minutes post-dose. Repeated measurements within-subject will be modeled using an unstructured covariance structure for within-subject error. In the case that the model fails to converge, a Huynh-Feldt error structure will be attempted, followed by an AR(1) structure. Error degrees of freedom will be calculated using a Kenward-Roger approximation. The difference estimate (rimegepant - placebo), SE, 95% CI, and p-value will be reported for 2 hours post-dose.

Intercurrent events of use of a non-study rescue medication at or before 2 hours post-dose, or if a subject fails to log their pain score at any time after study drug is administered through 2 hours post-dose, will be handled in the same manner as they are for the primary endpoint.

9.4.3.3 *Pain Freedom at 2 Hours*

The number of subjects that are pain free at 2 hours post-dose will be analyzed after first imputing missing data at 2 hours to be failure (NC = F). Additionally, subjects who use rescue medication on or before assessment of pain at 2 hours will also be assigned as failures (RM = F). The analysis will be done using a stratified Cochran-Mantel-Haenszel (CMH) test after imputation is done, with the stratification factor as use of daily medications / oral devices to reduce the intensity of TMD symptoms.

9.4.3.4 *Time to Onset of Meaningful Pain Relief*

Time to onset of meaningful pain relief post-dose will be defined as the first nominal timepoint at which a 30% reduction of pain from baseline on NRS is achieved. This will be analyzed using Kaplan-Meier methods for a “time to event” analysis. Rimegepant will be compared to placebo using a log-rank test which will compare the survival distributions. Intercurrent events will be handled in the same manner as they are for the primary endpoint.

9.4.3.5 *Time to Onset of Initial Pain Relief*

Time to onset of initial pain relief post-dose will be defined as the first nominal timepoint at which a 1-point reduction of pain from baseline on NRS is achieved. This will be analyzed using Kaplan-Meier methods for a “time to event” analysis. Rimegepant will be compared to placebo using a log-rank test which will compare the survival distributions. Intercurrent events will be handled in the same manner as they are for the primary endpoint.

9.4.3.6 *Rescue Medication Use through 24 Hours*

The number of subjects that use rescue medication through 24 hours post-dose will be analyzed using a stratified CMH test, with the stratification factor as use of daily medications/oral devices to reduce the intensity of TMD symptoms.

9.4.4 *Adjustment for Multiplicity*

Type 1 error is addressed in this study using a gatekeeping procedure. The significance of the primary endpoint is evaluated at the two-sided alpha level of 0.05. If the primary endpoint is significant, then the secondary endpoints are tested using Hochberg’s procedure.

CCI

9.4.5 *Missing Data*

For the primary and secondary endpoints of SPID-2, SPID-24, change in NRS from baseline, time to onset of meaningful pain relief, and time to onset of initial pain relief, subjects who fail to record their pain during the timeframe of interest for each endpoint will be considered

failures (NC = F) and this data will be imputed to the last available observation prior to the missing data occurrence.

For the secondary endpoint of proportion of subjects that are pain free at 2 hours post-dose, missing data at 2 hours post-dose will be imputed as a failure (NC = F), and these subjects will not be considered as having achieved pain freedom.

For the secondary endpoint of proportion of subjects who use rescue medication through 24 hours-post dose, there will be no imputation for missing data, the analysis will be based on non-missing, observed data.

Additional methods for handling of missing data, including sensitivity analyses, will be described in detail in the SAP.

9.4.6 *Rescue Medication*

For the primary and secondary endpoints of SPID-2, SPID-24, change in NRS from baseline, time to onset of meaningful pain relief, and time to onset of initial pain relief, use of non-study rescue medications on or before the time point of interest (2 hours post-dose or 24 hours post-dose) will be handled as failures (RM = F). Specifically, the assumption will be that once the subject has used a rescue medication, their pain will not improve any further and these data points will be set to the last value recorded prior to the use of the rescue medication.

For the secondary endpoint of pain freedom at 2 hours post-dose, subjects that take rescue medication on or before the time point of interest (2 hours post-dose) will be considered as failures (RM = F).

Rescue medications are described in more detail in Section [5.5](#).

9.4.7 *Analysis of Safety*

The Investigators determine the intensity of AEs and the relationship of AEs to study therapy. The Investigators' terms are coded and grouped by system organ class using the latest version of the Medical Dictionary for Regulatory Activities (MedDRA) available. AEs are presented by system organ class and preferred term, ordered by the overall frequency of events. If a subject had an adverse event with different intensities over time, then only the greatest intensity is reported.

AEs are tabulated in all treated subjects. SAEs occurring in subjects enrolled but not treated are listed. Deaths are listed for enrolled subjects without regard to onset.

The frequencies of the following safety events are summarized by treatment regimen, and overall, for treated subjects: SAEs; all AEs, AEs by intensity; and AEs by relatedness.

Clinically significant laboratory test abnormalities will be identified as Grade 3 to 4 laboratory test results graded according to numeric laboratory test criteria in Common Terminology Criteria for Adverse Events (CTCAE) Version 5.0 (2017), if available. Otherwise, if CTCAE grades are not available, then results will be graded according to numeric laboratory test criteria in Division of AIDS (DAIDS) Table for Grading the Severity

of Adult and Pediatric Adverse Events Corrected Version 2.1 (2017). If a subject has a laboratory test abnormality with different toxicity grades over time, then only the highest toxicity grade will be reported.

Further safety analyses will be described in the statistical analysis plan.

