9.2 Sample Size

If 80% of the 200 randomized (100 per treatment arm) treat with study drug, we expect roughly 160 total or 80 per treatment group in the randomized and treated population for analysis.

Assuming rimegepant provides a 2-point reduction in NRS pain, and a 1.5-point advantage over placebo on the primary endpoint, and a common standard deviation of 3.0, then the study will have roughly 88% power on the primary endpoint.

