The pain intensity difference at each post-baseline timepoint (PID_i) is calculated by finding the difference between the NRS score at each timepoint (PI_i) from the baseline NRS score (PI_0).

$$PID_i = PI_i - PI_0$$

The SPID-2 will be calculated by multiplying the PID score at each post-dose timepoint by the duration (in hours) since the preceding timepoint, then summing the values over the 2 hours.

$$SPID - 2 = \sum_{i=1}^6 (T_i - T_{(i-1)}) * PID_i$$

Where $T_0 = 0$, T_i = the nominal time as described in Table 3, $T_{(i-1)}$ = the preceding nominal time, PID_i = PID score at time T_i

Table 3: NRS Collection Nominal Timepoints

NRS collection timepoint	i	T_i (hours)
15 minutes	1	0.25
30 minutes	2	0.50
45 minutes	3	0.75
60 minutes	4	1.00
90 minutes	5	1.50
2 hours	6	2.00
4 hours	7	4.00
8 hours	8	8.00
24 hours	9	24.00

The SPID-2 will be analyzed on the treated population using an analysis of covariance (ANCOVA) model, estimated by Restricted Maximum Likelihood (REML) that includes baseline NRS value as a covariate and treatment group and stratification factor (use of daily medications / oral devices to reduce the intensity of TMD symptoms) as the main effects. The least squares mean (LS mean), standard error (SE), and 95% confidence intervals (CI) for each treatment group will be estimated and reported, as well as the LS mean, SE, and 95% CI for the difference between treatment groups (rimegepant – placebo). Descriptive summaries of PID value at each measured timepoint will be presented by treatment group to include mean, SD, median, minimum, and maximum.

The intercurrent events of non-study rescue medication and failure to log NRS pain score are treated with a composite strategy. All assessments after rescue medication administration are set to the last observation prior to the time of rescue medication use. Any missing NRS assessment(s) will be imputed to the last non-missing observation prior to the missing assessment. For clarity, in the case of intermittent missing values, missing values will be imputed based on the last non-missing observation prior to the missing value or consecutive series of missing values; any subsequent non-missing values will not be imputed unless rescue medication was administered prior to that assessment. Subjects who mistakenly dose and thus have a missing baseline NRS assessment will have the missing baseline assessment imputed as the mean of the non-missing baseline assessments across subjects.

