6.3.3.3 Pain Freedom at 2 Hours

The number and percentage of subjects in the treated population that experience pain freedom at 2 hours post-dose are analyzed after first imputing missing data at 2 hours to be failure (NC [Non-completer] = F [Failure]). Additionally, subjects who use rescue medication on or before assessment of pain at 2 hours are also assigned as failures (RM [Rescue medication use] = F). If the time of first rescue medication is missing, subjects are considered as failures if the date of rescue medication is the same as the date of dosing.

The analysis is done using Mantel-Haenszel risk estimation after imputation is done, with the stratification factor as yes/no for use of daily medications / oral devices to reduce the intensity of TMD symptoms. If one category of stratification factor has sparse data (less than 5 subjects), then the stratification factor is removed. Pain freedom is defined as an NRS score of zero at 2 hours post-dose (yes or no).

Results presented from the analysis includes the following:

- Response rate (i.e., “n/N” and percentage), asymptotic standard error (ASE), and 95% CI by randomization stratum for each treatment group
- Response rate (i.e., “n/N” and percentage), ASE, and 95% CI for each treatment group
- Percentage difference between treatment groups (rimegepant – placebo), ASE and 95% CI by randomization stratum
- Stratified percentage difference between treatment groups (rimegepant – placebo), ASE and 95% CI

A forest plot is produced depicting the risk difference for pain freedom at 2 hours post dose. The risk difference for each stratum will be presented, as well as the overall common risk difference.

6.3.3.4 *Time to Onset of Meaningful Pain Relief*

Time to onset of meaningful pain relief post-dose is analyzed descriptively for the treated population using Kaplan-Meier methods. Meaningful pain relief is considered the event in these analyses and is defined as the first nominal timepoint at which a 30% reduction of pain from baseline on the NRS is achieved. For clarity, meaningful pain relief is a 2-point reduction in NRS (0-10) score for subjects with a baseline pain score of 6, 7, or 8, and a 3-point reduction in NRS (0-10) score for subjects with a baseline pain score of 9 or 10.

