The number and percentage of subjects that use rescue medication within 24 hours post-dose are analyzed. Subjects who used rescue medication as of 24 hours post-dose are deemed failures, and subjects who did not use rescue medication as of 24 hours are deemed successes. For clarity, failure is the event being modeled (i.e. rescue medication use within 24 hours) in this analysis.

Refer to Section 6.2.6.3 for the definition of rescue medication. A rescue medication would be deemed used as of 24 hours post-dose if the date/time of first rescue medication use is strictly } 24 hours after the date/time of dosing, notwithstanding Section 6.3.1 of the SAP. Subjects with a rescue medication start date on or before study drug start date/time + 24 hours and missing rescue medication start time are excluded. Subjects who report non-study medication on the Rescue Medication CRF with a missing rescue medication date, or a partial medication date that is consistent with being used within 24 hours of dosing, are also excluded. Regardless of the foregoing, if a subject has at least one rescue medication use with non-missing start time that is } 24 hours after the date/time of dosing, the subject will be included in the analyses and deemed a failure.

No analysis window around the 24-hour post-dose time point is used.

The analysis follows the same methodology set forth in Section 6.3.3.3. A forest plot is produced depicting the risk difference for rescue medication use within 24 hours post dose. The risk difference for each strata will be presented, as well as the overall common risk difference.

Time to rescue medication use through 24 hours post-dose is assessed by treatment group as follows:

- Kaplan-Meier plot and table using 2-hour time intervals (i.e., 0 to 2, > 2 to 4, ... , > 24). The Kaplan-Meier plot displays the percentage of subjects taking rescue medication

data without imputation and regardless of rescue medication use. In these tables of safety parameters, if a subject has multiple values in the end of treatment analysis visit window (see Section 7.3), then the last non-missing value measured in the analysis period is used. See Sections 6.3.4.1, 6.4.4.1, and 6.4.2.4 for further handling of ties on the same measurement date or time.

By-subject listings of safety parameters are described in subsections and identify on-treatment data.

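### The pain-freedom and rescue-use risk differences adjust for the randomisation stratum but not for baseline NRS, which is collected and already used in the SPID and 2-hour change models

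*Protocol*

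**What the plan says.** **Continuous endpoints.** The SPID-2 model in SAP 6.3.2.1 "includes baseline NRS value as a covariate and treatment group and stratification factor" as main effects. SPID-24 repeats it (SAP 6.3.3.1). The 2-hour change model also carries baseline NRS and the stratum (Protocol 9.4.3.2, SAP 6.3.3.2).

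**Binary endpoints.** Protocol 9.4.3.3 on pain freedom: "The analysis will be done using a stratified Cochran-Mantel-Haenszel (CMH) test after imputation is done, with the stratification factor as use of daily medications" and oral devices. Protocol 9.4.3.6 does the same for rescue use. SAP 6.3.3.3 now reads: "The analysis is done using Mantel-Haenszel risk estimation after imputation is done, with the stratification factor as yes/no". It reports the difference with an asymptotic standard error and 95% CI, and drops the stratum if one category has fewer than 5 subjects. For rescue use, SAP 6.3.3.6 says: "The analysis follows the same methodology set forth in Section 6.3.3.3". Baseline NRS appears in none of these.

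**Time to relief.** Protocol 9.4.3.4 and 9.4.3.5: "Rimegepant will be compared to placebo using a log-rank test which will compare the survival distributions". No stratum or covariate is named. The SAP v2.0 revision history removes this comparison, and SAP 6.3.3.4 and 6.3.3.5 describe each arm by Kaplan-Meier.

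**Status.** SAP 1 records early termination in 1Q2023 for low enrolment. SAP 5 says that the significance of primary and secondary endpoints will not be evaluated.

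**The concern.** Pain freedom means NRS 0 at 2 hours, so it needs a 6-point fall from a baseline of 6 and a 10-point fall from 10. Baseline is therefore likely to predict it, and may predict rescue use as well. With no significance testing left, the risk difference and its interval are the result for these two endpoints. An analysis without baseline NRS leaves chance imbalance in that estimate and gives up whatever precision baseline could provide. The early stop makes chance imbalance more likely than at the planned size. If the sparse-stratum rule is triggered, the binary comparisons have no adjustment at all, while the SPID and change models still adjust for baseline.

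**Working it through.** **1. The plan's own figure.** Protocol 9.2: "Assuming rimegepant provides a 2-point reduction in NRS pain, and a 1.5-point advantage over placebo on the primary endpoint", with "a common standard deviation of 3.0", 80 per arm; Protocol 9.4.4: "The significance of the primary endpoint is evaluated at the two-sided alpha level of 0.05". SE = 3.0 × √(2/80) = 0.474; 1.5/0.474 = 3.16; power = Φ(3.16 − 1.96) = 88.5% (88.2% with the t distribution). The stated 88% reproduces. It concerns SPID-2 only; the documents give no rates or power for the binary endpoints, so everything below rests on assumptions.

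**2. How far baseline could drive pain freedom.** Assume the planning figures apply to the 2-hour NRS change: normal, mean fall 2.0 on rimegepant and 0.5 on placebo, SD 3.0. Then P(NRS 0) = Φ((mean fall − (b − 0.5))/3).

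| Baseline b | Rimegepant | Placebo |
|---|---|---|
| 6 | 12.2% | 4.8% |
| 7 | 6.7% | 2.3% |
| 8 | 3.3% | 1.0% |
| 9 | 1.5% | 0.4% |
| 10 | 0.6% | 0.1% |

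Over three assumed baseline distributions, baseline explains 1% to 8% of the variance of the pain-free indicator. In large samples the variance of an adjusted estimate is then about 0.92 to 0.99 of the unadjusted one. This figure is for pain freedom only.

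**3. How likely an imbalance is.** Dosing requires NRS of at least 6, so baselines should lie in 6 to 10. Assume a baseline SD of 1.2 to 1.4 (a uniform spread over 6 to 10 gives 1.41). The SE of the difference in means is SD × √(2/n).

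| Per arm | SE | Chance of a gap of 1 point or more |
|---|---|---|
| 80 | 0.19 to 0.22 | under 0.001% |
| 20 | 0.38 to 0.45 | about 1% to 3% |
| 10 | 0.54 to 0.63 | about 6% to 11% |

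A half-point gap is less rare: with SD 1.2, about 1% at 80 per arm, 19% at 20 and 35% at 10. Under step 2, one baseline point moves the pain-free rate by about 1 to 4 percentage points. A one-SE imbalance therefore moves it by about 0.2 to 0.9 points at 80 per arm (0.19 × 1 to 0.22 × 4) and 0.4 to 1.8 points at 20 per arm (0.38 × 1 to 0.45 × 4).

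**4. What adjustment gains or costs.** The linear model with HC3 errors was simulated under the null at 15 to 80 per arm, with assumed rates of 10% and 40% and a baseline effect from none to strong. Against stratum-only adjustment, the variance changed by about +4% to −18%, and type I error stayed at or below 5%. The gain was little or none at the rare rate. In interval width this is √1.04 = 1.02 (2% wider) to √0.82 = 0.91 (9% narrower). The +4% agrees with the usual cost of one uninformative covariate, about 1/(N − 5) after three parameters: 1/25 = 4% at 15 per arm and 1/155 = 0.6% at 80 per arm. A similar run at rates of 15% and 40%, 20 and 80 per arm, with log-odds of 0 to 0.9 per NRS point, gave +3% to −12% for pain freedom and +2% to −25% for rescue. The size depends on how prognostic baseline is.

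**5. The same comparison as power, for scale.** At 80 per arm, stratified CMH against a logistic score test with baseline added:
- Pain freedom, 10% vs 25%: 71% and 72% with no baseline effect; 72% and 77% at an odds ratio of 0.4 per NRS point.
- Rescue, 50% vs 30%: 74% and 74% with no effect; 72% and 84% at an odds ratio of 2.5 per point.

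In the pain-freedom null runs the planned CMH test rejected in 3.8% to 5.4% of trials, so it is valid.

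**6. If a log-rank comparison were restored.** At 80 per arm, hazard ratio 1.6 and equal strata, power without and with stratification is 72% and 73% at a stratum hazard ratio of 1.5, 71% and 75% at 2, and 64% and 77% at 3. The two are equal if the stratum is not prognostic.

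**The case against.** The strongest defence is that stratified Mantel-Haenszel is standard and valid and respects the randomisation. The entry rule narrows the baseline range and so limits what adjustment can gain. The SAP expects sparse data, and a covariate model with few events can be unstable. All of this stands. It is why the adjusted estimate should sit beside the Mantel-Haenszel result, and why a linear model is preferable to a logistic one that may not converge. It does not remove the case for adjustment. SAP 6.3.2.1 and 7.5 impute baseline NRS when it is missing after mistaken dosing, so adjustment excludes nobody, and the documents give no reason for treating the binary endpoints differently.

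Two stronger readings are tempting and not supported.

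- A reader might infer that the time-to-relief analysis is defective for using an unstratified log-rank test. SAP v2.0 has no such test. The Protocol is silent on strata and does not exclude them; it refers to the SAP for complete details. The Core SAP, which governs where the SAP is silent, is not available here.
- A reader might infer that baseline imbalance could seriously distort the pain-free difference. That needs a gap of about a point, which step 3 shows to be very unlikely except in very small arms. The achieved sample size is not in the documents.

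**Conclusion.** The concern holds as a minor point of efficiency. The two binary risk differences omit a baseline value that the same SAP uses for its SPID and 2-hour change models. The planned estimates are valid. The loss is some precision and uncorrected chance imbalance: a variance change of about +4% to −18% from adding baseline under assumed rates of 10% and 40%, and little or no gain if pain freedom is rare. These figures rest on assumed event rates, baseline spread and prognostic strength, none of which the documents give. With no significance testing in SAP v2.0, the practical effect is on the width and centring of two confidence intervals. The time-to-relief analysis in the current SAP is not at fault.

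**What to change.** In SAP 6.3.3.3 and 6.3.3.6, add a risk difference (rimegepant minus placebo) with 95% CI from a linear model of the 0/1 outcome on treatment, randomisation stratum and baseline NRS, with HC3 standard errors. Report it beside the Mantel-Haenszel difference, and state in advance that Mantel-Haenszel stands alone if events are too few to fit the model. Keep baseline NRS in the model if the stratum is dropped for sparse data.

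If a between-arm comparison under Protocol 9.4.3.4 or 9.4.3.5 is restored, stratify it by the randomisation stratum.

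The cost is a few lines of SAP text and code on data already collected. The downside is one more parameter, with up to about 4% more variance in very small arms if baseline is not prognostic.
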